9.2.3 Medical History

Medical history will be coded by using the Medical Dictionary for Regulatory Activities (MedDRA). For the FAS, medical history will be summarized descriptively by system organ class and preferred term. The corresponding data listing will also be provided.

In addition, the number of subjects reported to have had positive cultures for respiratory pathogens within the 2 years prior to screening (i.e., answered yes on the respiratory microbiology form) will be summarized for the FAS. The corresponding data listing will be provided. Hospitalization and clinic visit history in the year prior to the signing of informed consent will be listed.

9.2.4 Prior and Concomitant Medications

Medications will be coded using the World Health Organization Drug Dictionary (WHO-DD) and categorized as follows:

Prior medication: any medication that was administered during the 56 days before the first dose of study drug in the Treatment Period but not in the Run-in Period. For subjects who discontinue during the Run-in Period and whose first dose of study drug in the Treatment Period is not available, prior medication will be any medication that was administered during the 56 days before the last dose of study drug in the Run-in Period but before the first dose in the Run-in Period.

Concomitant medication during the Run-in Period: medication continued or newly received during the TE period for the Run-in Period.

Concomitant medication during the Treatment Period: medication continued or newly received during the TE period for the Treatment Period.

Post-treatment medication: medication continued or newly received after:

- the TE period for the Run-in Period if the subject did not receive study drug in the Treatment Period.
- the TE period for the Treatment Period for subjects who received study drug in the Treatment Period.

A given medication may be classified as any combination of the above categories, for example, prior and concomitant during the Run-in Period, concomitant during the Treatment Period and post-treatment, or concomitant for both periods and post-treatment.

If a medication has completely missing or partially missing start/stop date and if it cannot be determined whether it was taken before the first dose date of study drug, concomitantly, or after the TE period, it will be classified as prior, concomitant for both periods, and post-treatment. Details for imputing missing or partial start and/or stop dates of medication are described in [Appendix B](#).

Prior medications and concomitant medications will be summarized descriptively for FAS using frequency tables by: 1) treatment group and overall, preferred name (PN); and 2) treatment group and overall, anatomic class (ATC) level 1, ATC level 2, and PN.

Prior and concomitant medication during the Run-in Period will be summarized together in one summary table. Post-treatment medications will be listed in the all medication listing.

9.2.5 Study Drug Exposure

Study drug exposure will be summarized for the Treatment Period only based on the Safety Set for the Treatment Period, and will be presented by treatment group and overall.

Duration of study drug exposure (in days) will be calculated as: last dose date of study drug in the Treatment Period – first dose date of study drug in the Treatment Period + 1, regardless of study drug interruption, and will be summarized descriptively.

Study drug exposure (in weeks) will be summarized descriptively by the number of subjects (n), mean, SD, median, min, and max. It will also be summarized by interval: ≤ 2 weeks, $>2 - \leq 4$ weeks, and > 4 weeks, using counts and percentages. Additionally, the total study drug exposure, defined as the sum total of the study drug exposure across all subjects (in patient-weeks), will be provided.

9.2.6 Study Drug Compliance

Study drug compliance will be summarized for the Treatment Period only based on the FAS, and will be presented by treatment group and overall.

Study drug compliance will be calculated as: $100 \times [1 - (\text{total number of days of study drug interruption during the Treatment Period}) / (\text{duration of study drug exposure in days during the Treatment Period})]$. A study drug interruption on a given day is defined as an interruption of any study drugs on that day. A study drug interruption that continues through the end of the study participation (i.e., subject does not resume study drug before the end of the study participation) will not be included in the compliance calculation.

Study drug compliance will be summarized descriptively by the number of subjects (n), mean, SD, median, min, and max. It will also be summarized in categories: $<80\%$ and $\geq 80\%$ using frequency tables.

In addition, percentage of tablets taken will be calculated using the following formula:
$$100 \times [(total\ number\ of\ tablets\ dispensed\ for\ the\ Treatment\ Period) - (total\ number\ of\ tablets\ returned\ for\ the\ Treatment\ Period)] / (total\ number\ of\ tablets\ planned\ to\ be\ taken\ per\ day \times duration\ of\ study\ drug\ exposure\ in\ days\ for\ the\ Treatment\ Period).$$
 Summary similar to those for the study drug compliance will be produced based on the FAS.

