### 12.3.2.4 Study Drug Exposure and Compliance

Study drug exposure and compliance will be summarized for the Treatment Period only.

Study drug exposure will be summarized overall and by treatment group, based on the Safety Set in terms of the duration of treatment a subject received (in days), defined as the last day – the first day of study drug plus 1, regardless of study drug interruption.

Study drug compliance will be summarized overall and by treatment group based on the FAS, and will be calculated as:  $100 \times [1 - (\text{total number of days of study drug interruption}) / (\text{duration of study drug exposure in days})]$ . A study drug interruption on a given day is defined as an interruption of any study drug on that day.

In addition, percentage of tablets taken will also be summarized overall and by treatment group based on the FAS, and will be calculated as  $100 \times [(\text{total number of tablets dispensed for the Treatment Period}) - (\text{total number of tablets returned for the Treatment Period})] / (\text{total number of tablets planned to be taken per day} \times \text{duration of study drug exposure in days for the Treatment Period})$ .

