3 MODIFICATIONS

3.1 Modifications to the Approved Clinical Study Protocol

Not Applicable.

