9.2 Background Characteristics

9.2.1 Subject Disposition

A disposition table will be provided for the Run-in Period with the following categories:

- All Subjects Set
- Safety Set for the Run-in Period

The number and percentage (based on Safety Set for the Run-in Period) of subjects in each of the following disposition categories will be summarized:

- Prematurely discontinued treatment before randomization and the reason for treatment discontinuation
- Prematurely discontinued study before randomization and the reason for study discontinuation

A separate disposition table will be provided for the Treatment Period with the following categories:

- Full Analysis Set
- Safety Set for the Treatment Period
- Randomized
- Randomized but not dosed in the Treatment Period
- Randomized or dosed in the Treatment Period

The number and percentage (based on FAS) of subjects in each of the following disposition categories will be summarized by treatment group and overall:

- Completed study drug treatment
- Prematurely discontinued treatment and the reason for discontinuation (i.e., discontinued all study drugs)
- Completed study
- Prematurely discontinued the study and the reason for discontinuation
- Rollover to the open-label study

A listing will be provided for subjects who discontinued treatment (including both the Run-in Period and Treatment Period) or who discontinued study with reasons for discontinuation.

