9.2.7 Important Protocol Deviations

An important protocol deviation (IPD) is a deviation that may significantly affect the completeness, accuracy, or reliability of the study data or that may significantly affect a subject's rights, safety, or well-being. IPD rules will be developed and finalized before database lock.

The protocol deviations that should be considered as potential IPDs include, but are not limited to:

- Subject was enrolled in the study despite the violation of inclusion/exclusion criteria
- Subject was less than 80% compliant with study drug for non-safety reasons
- Subject received prohibited concomitant medications
- Subject received the wrong treatment or incorrect doses
- Subject remained in the study despite meeting withdrawal criteria

Occurrence of any of these events should be considered as potential IPDs, but a blinded team should categorize them as IPDs only if they have the potential to significantly affect the completeness, accuracy, or reliability of the study data or that may significantly affect a subject's rights, safety, or well-being.

IPDs (from the clinical database or from the site deviation log) will be summarized descriptively based on the FAS and presented by treatment group and overall. Additionally, IPDs will be provided in an individual subject data listing.

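### SAP 9.2.6 leaves out never-resumed interruptions, so read literally it scores a subject who permanently stops one study drug but continues another as 100% compliant

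*SAP*

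**What the plan says.** Protocol 12.3.2.4 defines compliance as 100 x [1 - interruption days / exposure days] and says: "A study drug interruption on a given day is defined as an interruption of any study drug on that day". It makes no exception for interruptions that are never resumed.

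SAP 9.2.6 keeps the formula and the any-drug definition ("A study drug interruption on a given day is defined as an interruption of any study drugs on that day") and adds a clause. "A study drug interruption that continues through the end of the study participation", glossed as the case where the "subject does not resume study drug before the end of the study participation", "will not be included in the compliance calculation". SAP 3.1, which is for modifications to the protocol, reads "Not Applicable".

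Four other provisions matter:
- **Exposure.** SAP 9.2.5 counts from the first to the last dose date of study drug, whatever the gaps. Protocol section 10 includes evening IVA in study drug for the Treatment Period.
- **Disposition.** SAP 9.2.1 has the category "Prematurely discontinued treatment and the reason for discontinuation (i.e., discontinued all study drugs"), so stopping one component is not a discontinuation there.
- **Deviation screen.** SAP 9.2.7 lists as a potential important deviation: "Subject was less than 80% compliant with study drug for non-safety reasons".
- **Second measure.** SAP 9.2.6 also reports percentage of tablets taken, with a summary like the one for compliance.

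**The concern.** The numerator and denominator follow different rules. An interruption starts when any one drug is missed, but exposure ends only when every drug has stopped. For a subject who permanently stops one component and keeps taking another, the denominator stays at full length while every missed day is dropped from the numerator. The longest possible gap then counts as no gap.

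The SAP itself expects partial stopping: its adverse event overview (SAP 9.4.1) counts events leading to discontinuation of any study drug. Such a subject could be a drug discontinuation in the adverse event table, not one in the disposition table, and fully compliant in the compliance table.

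At stake are the compliance summary, its category below 80%, and possibly the deviation screen.

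**Working it through.** The plan states no compliance figure, so there is none to reproduce. The check applies both formulas to one example.

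**Inputs**
- Tablets per day (Protocol 9.6.1): 2 triple-combination or placebo plus 1 TEZ/IVA or placebo in the morning, and 1 IVA in the evening; 4 in total.
- Last planned dose (Protocol Table 3-2): the evening before the Week 4 Visit. With the SAP Appendix A target of Day 29, that is Day 28.
- Example (assumed): all morning tablets last taken on Day 4, IVA taken every evening to Day 28, all untaken tablets returned.

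**Compliance**
1. Exposure = 28 - 1 + 1 = 28 days.
2. Days with any study drug interrupted, up to the last dose = 28 - 4 = 24.
3. Protocol formula: 100 x (1 - 24/28) = 14.3%.
4. SAP formula, clause read literally: the 24-day interruption is never resumed, so 0 days count, and 100 x (1 - 0/28) = 100%.

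**Percentage of tablets taken** (planned: 4 x 28 = 112)
- All morning tablets stopped: 4 x 4 + 24 x 1 = 40; 40/112 = 35.7%.
- Only the triple-combination tablets (or their placebo) stopped: 4 x 4 + 24 x 2 = 64; 64/112 = 57.1%. The compliance results are unchanged.

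**Visit window.** The Week 4 Visit may move by 5 days either way, so the last IVA dose may fall on Day 23 to Day 33. The protocol formula then gives 100 x (1 - 19/23) = 17.4% to 100 x (1 - 29/33) = 12.1%. The literal SAP rule gives 100% throughout.

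**Ordering.** Suppose the same subject resumes the morning tablets on Day 28. Days 5 to 27 are interrupted, 23 days, and the SAP gives 100 x (1 - 23/28) = 17.9%. The subject who never resumes, and so took less drug, scores 100%.

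**All drugs stopped after Day 4.** Exposure is 4 days with no interruption inside it, so compliance is 100% with the clause. If the 24 days from Day 5 to Day 28 were counted over that exposure, the result would be 100 x (1 - 24/4) = -500%. Here the clause is needed.

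**The case against.** **The clause has a proper purpose.** As the last step of the working shows, it stops days after the end of exposure from entering the numerator. This stands, and it is why simply deleting the clause would be a poor remedy.

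**The gloss allows another reading.** It speaks of a subject who does not resume study drug. A subject taking IVA every evening is arguably still on study drug, so the clause would not apply and the 24 days would count. The any-drug definition in the sentence before favours the literal reading, but the text does not settle it. Two programmers could report 14.3% or 100% for the same subject.

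**Partial stopping is not hidden.** Percentage of tablets taken falls well below 80% in the example and has its own summary, and adverse-event-driven partial stops appear in SAP 9.4.1. A reader might infer that the reported tables could not reveal drug not taken; the second measure shows otherwise. What remains is a conflict between two measures with no rule for which governs the screen. The deviation list in SAP 9.2.7 is also open-ended and includes incorrect doses.

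**A wider reading is tempting.** A reader might infer that the clause also masks subjects who stop everything early without a recorded discontinuation. For a subject who stops after Day 14, both measures are indeed 100% (tablets 56/56). But the protocol formula also gives 100%, because its own denominator ends at the last dose, and the SAP 9.2.5 exposure table would place the subject at 2 weeks or less. That is not an effect of this clause.

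**Partial stopping may be rare.** Protocol 9.8 states its interruption and stopping rules for study drug as a whole, not by component. The documents give no expected frequency and no basis for supposing that it differs between arms.

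**The protocol defers statistical detail to the SAP.** True, but this detail changes the result of a formula that the protocol writes out.

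**Conclusion.** The point holds for partial permanent discontinuation. Read literally, SAP 9.2.6 returns 100% where the protocol formula returns 14.3% in the example, and the SAP's own tablet measure returns 35.7% or 57.1%. The figures rest on morning tablets last taken on Day 4, IVA to Day 28, full return of untaken tablets, and the literal reading of the clause.

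The reach is small. Compliance is descriptive. Efficacy analyses use the Full Analysis Set, no per-protocol set is defined, and no efficacy model uses compliance, so the primary result is unaffected. With 50 subjects per arm, each such subject is 1/50 = 2% of an arm in the compliance categories. The number of such subjects cannot be derived from the documents, and they do not support a claim of bias between arms. It is still a stated rule that gives a wrong figure, and a short amendment corrects it.

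**What to change.** Amend the SAP before database lock:

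1. In 9.2.6, limit the exclusion to days after the last dose of all study drugs. Days off any one study drug up to that date then count as interruption, as in the protocol formula. This keeps the protection for subjects who stop everything and removes the ambiguity in the gloss.
2. In 9.2.7, state whether the 80% screen uses study drug compliance or percentage of tablets taken.
3. In 3.1, record the clause as an addition to the formula in Protocol 12.3.2.4.

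The cost is SAP wording and minor programming on data already collected, with no change to trial conduct. The downside is that reported compliance may be slightly lower.

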9.2.7 Important Protocol Deviations

An important protocol deviation (IPD) is a deviation that may significantly affect the completeness, accuracy, or reliability of the study data or that may significantly affect a subject's rights, safety, or well-being. IPD rules will be developed and finalized before database lock.

The protocol deviations that should be considered as potential IPDs include, but are not limited to:

- Subject was enrolled in the study despite the violation of inclusion/exclusion criteria
- Subject was less than 80% compliant with study drug for non-safety reasons
- Subject received prohibited concomitant medications
- Subject received the wrong treatment or incorrect doses
- Subject remained in the study despite meeting withdrawal criteria

Occurrence of any of these events should be considered as potential IPDs, but a blinded team should categorize them as IPDs only if they have the potential to significantly affect the completeness, accuracy, or reliability of the study data or that may significantly affect a subject's rights, safety, or well-being.

IPDs (from the clinical database or from the site deviation log) will be summarized descriptively based on the FAS and presented by treatment group and overall. Additionally, IPDs will be provided in an individual subject data listing.

9.3 Efficacy Analysis

Unless otherwise defined, all efficacy analyses described in this section will be based on the FAS.

9.3.1 Analysis of Primary Efficacy Variable

9.3.1.1 Definition of Variable

The primary efficacy variable is the absolute change in ppFEV₁ from baseline at Week 4. Percent predicted FEV₁ is the ratio of FEV₁ (L) to the predicted FEV₁ (L), expressed as a percentage. The predicted FEV₁ will be calculated using the Global Lung Function Initiative¹ (GLI); details are in [Appendix C](#).

9.3.1.2 Primary Analysis

The primary analysis will be performed using a mixed-effects model for repeated measures (MMRM) with the absolute change from baseline at Day 15 and Week 4 as the dependent variable. The model will include treatment group, visit, and treatment-by-visit interaction as fixed effects, with continuous baseline ppFEV₁, and age at screening (<18 versus ≥18 years of age) as covariates. The model will be estimated using restricted maximum likelihood.

Denominator degrees of freedom for the F -test for fixed effects will be estimated using the Kenward-Roger approximation². An unstructured covariance structure will be used to model the within-subject errors. If the model estimation does not converge, a compound symmetry covariance structure will be used instead. Conditional on the observed data and covariates, missing data will be assumed to be missing at random; consequently, no imputation of missing data will be performed.

The primary result obtained from the model will be the estimated treatment difference at Week 4. The adjusted means with 2-sided 95% confidence intervals and 2-sided P values will be provided. Furthermore, the treatment difference at each post-baseline visit obtained from the model will also be provided.

The adjusted mean (with SE) obtained from the MMRM analysis at each post-baseline visit up to Week 4 will be plotted by treatment group.

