**Statistical Analyses**

The primary efficacy endpoint is the absolute change in ppFEV1 from baseline at Week 4. The primary null hypothesis to be tested is that the mean absolute change in ppFEV1 from baseline at Week 4 is the same for the TC and TEZ/IVA treatment groups. The null hypothesis will be tested at a 2-sided significance level of 0.05.

Assuming a within-group SD of 7 percentage points and a 5% dropout rate at Week 4, a sample size of 50 subjects in each treatment group for a total of 100 subjects will have approximately 93% power to detect a difference of 5.0 percentage points for the mean absolute change in ppFEV1 from baseline at Week 4 between the 2 treatment groups, based on a 2-sided 2-sample *t*-test at a significance level of 0.05.

The primary analysis will be based on a mixed-effects model for repeated measures (MMRM). The model will include the absolute change from baseline in ppFEV1 at Day 15 and Week 4 as the dependent variable; treatment group, visit, and treatment-by-visit as fixed effects; with continuous baseline ppFEV1 and age at screening (<18 versus ≥18 years of age) as covariates; and an unstructured covariance structure for the within-subject errors.

The primary result obtained from the model will be the estimated treatment difference at Week 4. The adjusted mean with a 2-sided 95% CI and a 2-sided *P* value will be provided.

The safety endpoints include AEs, clinical laboratory values, ECGs, vital signs, and pulse oximetry through the Safety Follow-up Visit. The safety analysis will be descriptive only.

**IDMC Reviews** An independent data monitoring committee (IDMC) will conduct safety review of study data as outlined in the IDMC charter.

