**Table 3-2 VX17-445-103: TEZ/IVA Run-in Period, Treatment Period, and Safety Follow-up Visit**

Event/Assessment a	TEZ/IVA Run-in Period (4 Weeks)		Treatment Period (4 Weeks)			ETT Visit b	Safety Follow-up Visit 28 (± 7) Days After the Last Dose of Study Drug (If Applicable) c
	Day -28 ± 1 Day	Day -14 (Day -15 to Day -3)	Day 1 d	Day 15 ± 3 Days	Week 4 ± 5 Days		
Vital signs j	X		X	X	X	X	X
Pulse oximetry j	X		X	X	X	X	X
Spirometry k		X	X	X	X	X	X
Sweat chloride l		X	X	X	X	X	
Urinalysis	X		X		X	X	X
Hematology	X m		X m	X	X	X	X
Coagulation	X m		X m		X	X	X
Serum chemistry	X m		X m	X	X	X	X
PK sampling n			X		X	X	

j Vital signs and pulse oximetry will be collected before dosing and after the subject has been at rest for at least 5 minutes.

k Spirometry assessments must be performed before study drug dosing (see [Section 9.6.1](#)) and should be performed pre-bronchodilator ([Section 11.6.1](#)) at approximately the same time at each visit.

l Sweat chloride collection will occur before study drug dosing ([Section 11.4](#)). At each time point, 2 samples will be collected, 1 from each arm (left and right).

m Blood samples will be collected before the first dose of study drug in each study period.

n The Day 1 predose PK sample must be collected before dosing. The Week 4 predose PK sample must be collected within 60 minutes before dosing for subjects who are receiving their first dose of study drug in an open-label study on the same day as the Week 4 Visit. For subjects who are not entering an open-label study on the same day as the Week 4 Visit, the Week 4 sample should be collected approximately 12 hours after the evening dose of IVA on the day prior to the Week 4 Visit ([Section 11.3.1](#)).

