### 9.1.2 Tezacaftor/Ivacaftor Run-in Period

The TEZ/IVA Run-in Period has a 4-week duration and is designed to establish a reliable on-treatment (TEZ/IVA) baseline for the Treatment Period. The first dose of open-label TEZ/IVA will be administered at the Day -28 Visit. The last dose of open-label TEZ/IVA will be administered in the evening on Day -1 (1 day before the Day 1 Visit).

On Day -14, spirometry and SwCl will be assessed. The Day -14 spirometry assessment will be used for stratification of randomization ([Section 9.2](#)).

Subjects who prematurely discontinue study drug treatment during the Run-in Period will not be randomized or participate in the Treatment Period ([Section 9.1.5.1](#)).

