#### **12.3.3.1 Analysis of Primary Variable**

The primary efficacy variable is the absolute change in ppFEV1 from baseline at Week 4. The analysis of this variable will be performed using a mixed-effects model for repeated measures (MMRM) with absolute change from baseline in ppFEV1 at Day 15 and Week 4 as the dependent variable. The model will include treatment group, visit, and treatment-by-visit interaction as fixed effects, with continuous baseline ppFEV1 and age at screening (<18 versus ≥18 years of age) as covariates. The model will be estimated using restricted maximum likelihood.

Denominator degrees of freedom for the *F* test for fixed effects will be estimated using the Kenward-Roger approximation. An unstructured covariance structure will be used to model the within-subject errors. If the model estimation does not converge, a compound symmetry covariance structure will be used instead. Conditional on the observed data and covariates, missing data will be assumed to be missing at random; consequently, no imputation of missing data will be performed.

The primary result obtained from the model will be the estimated treatment difference at Week 4. The adjusted mean with a 2-sided 95% CI and a 2-sided *P* value will be provided. Furthermore, the treatment difference at each post-baseline visit will also be provided, obtained from the model.

Sensitivity analyses for handling missing data will be described in the SAP.

Supportive analyses and subgroup analyses by selected baseline characteristics will also be described in the SAP.

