9 STATISTICAL ANALYSIS

9.1 General Considerations

The Schedule of Assessments is provided in Section 3 of CSP. The precision standards for reporting safety and efficacy variables are provided in an internal Biometrics document that specifies the programming rules including the precision for derived variables.

Continuous variables will be summarized using the following descriptive summary statistics: the number of subjects (n), mean, SD, median, minimum value (min), and maximum value (max).

Categorical variables will be summarized using counts and percentages. Percentages will be presented to 1 decimal place.

Baseline value, unless otherwise specified, is defined as the most recent non-missing measurement (scheduled or unscheduled) collected before the first dose of study drug in the Treatment Period.

Absolute change from baseline will be calculated as post-baseline value – baseline value.

Relative change from baseline will be calculated as (post-baseline value – baseline value)/baseline value.

The **Treatment-emergent (TE) Period for the Run-in Period** will be from the first dose of study drug in the Run-in Period to

- 1) for subjects who complete the run-in period and continue to the Treatment Period, the first dose of study drug in the Treatment Period, or

- 2) for subjects who do not continue to the Treatment Period, either 28 days after the last dose date of study drug in the Run-in Period, or to the completion of study participation date, whichever occurs first.

The **TE Period for the Treatment Period** will include the time from the first dose date of study drug in the Treatment Period (TC or placebo + TEZ/IVA) to 28 days after the last dose of the study drug or to the completion of study participation date, whichever occurs first.

Unscheduled visits: Unscheduled visit measurements will be included in analysis as follows:

- 1) In scheduled visit windows per specified visit windowing rules
- 2) In the derivation of baseline and last on-treatment measurements
- 3) In the derivation of maximum and minimum values during TE period, and maximum and minimum change from baseline values during TE period for safety analyses
- 4) In individual subject data listings as appropriate

Visit windowing rules: The analysis visit windows for protocol-defined visits are provided in [Appendix A](#).

Incomplete/missing data will not be imputed, unless specified otherwise.

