9.3.1.3 Supportive Analysis

There will be no supportive analysis for the primary efficacy endpoint.

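### Should the primary MMRM also adjust for the Day -14 ppFEV1 that is already collected?

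*SAP*

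**What the plan says.** The primary model is given in three places with the same content. SAP 9.3.1.2 reads "The model will include treatment group, visit, and treatment-by-visit interaction as fixed effects, with continuous baseline ppFEV₁, and age at screening" (split at 18 years). Protocol 12.3.3.1 agrees: "The model will include treatment group, visit, and treatment-by-visit interaction as fixed effects", with the same two covariates. The protocol synopsis has "treatment group, visit, and treatment-by-visit as fixed effects" and again the same covariates.

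SAP 9.1 defines baseline as "the most recent non-missing measurement (scheduled or unscheduled) collected before the first dose of study drug in the Treatment Period". It is one reading, not a run-in average.

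Protocol 9.1.2 schedules another reading during the run-in: "On Day -14, spirometry and SwCl will be assessed". Table 3-2 lets that visit fall anywhere from Day -15 to Day -3. The value is dichotomised at 70 for stratification (protocol 9.2, SAP 7.3) and tabulated by stratum (SAP 9.2.2). As a continuous measure it is in none of the efficacy models shown, unless Day 1 is missing and it becomes the baseline. SAP 9.3.1.3 adds: "There will be no supportive analysis for the primary efficacy endpoint". Some text is redacted, so this describes only what is visible.

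**The concern.** A single spirometry reading carries visit-to-visit noise. A second reading before randomisation, on the same background drug and meant to be pre-bronchodilator like later visits (protocol 11.6.1), should say more about a subject's underlying level and so remove some residual variance. Protocol 9.3.1 itself says that response may depend on ppFEV1 before triple therapy and chose Day -14 as a stratifier for that reason. The age stratum is carried into the model as it stands, but the Day -14 measurement is not.

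Adjusting for a pre-randomisation value does not bias the treatment estimate, and the data cost nothing extra. What is at stake is the width of the CI for the Week 4 difference. The success decision is not at stake, because the planned power is already high.

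**Working it through.** **Planned power.** Inputs from SAP 7.2: difference 5.0, SD 7, 50 per arm, 5% dropout, two-sided 0.05. Then n = 50 × 0.95 = 47.5 per arm, and the noncentrality is 5/(7 × √(2/47.5)) = 3.481 on 93 df. Power is 93.1%, which matches the stated figure. At the Phase 2 contrast in protocol 9.3.2 (11.0 − 0.4 = 10.6 points) it exceeds 99.9%.

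**Model for the gain.** Let Day -14 be Y0 = b + e0, Day 1 be Y1 = b + e1, and Week 4 be W = b + e2 + t. The outcome is C = W − Y1, with variance 7² = 49. Noise e has correlation r per 14 days, and a share s of the 49 is noise:

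2·var(e)·(1 − r²) = 49s, and var(t) = 49(1 − s).

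The documents give none of SD(b), s or r. Assumed ranges are SD(b) 12 to 15, s 25% to 100%, and r 0 to 0.8.

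**Middle case (SD(b) 15, s = 50%, r = 0.5).**
- var(e) = 24.5/(2 × 0.75) = 16.333, so Var(Y0) = Var(Y1) = 225 + 16.333 = 241.333.
- Cov(C, Y1) = 16.333 × (0.25 − 1) = −12.25. Var(C | Y1) = 49 − 12.25²/241.333 = 48.38.
- Cov(C, Y0) = 16.333 × (0.125 − 0.5) = −6.125. Cov(Y0, Y1) = 225 + 8.167 = 233.167.
- Partial covariance of C and Y0 given Y1: −6.125 + 12.25 × 233.167/241.333 = 5.711. Var(Y0 | Y1) = 241.333 − 233.167²/241.333 = 16.06.
- Var(C | Y1, Y0) = 48.38 − 5.711²/16.06 = 46.35, a cut of 4.2%.
- The extra covariate costs a factor of 1 + 1/91, about 1.1%. Net gain: 1 − (46.35 × 92/91)/48.38 = 3.1%.
- Half-width t(0.975) × √(v × 2/47.5) goes from 2.835 to 2.790, which is 0.045 points or 1.6%.

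**Other values of r (SD(b) 15, s = 50%; the range column covers all assumed SD(b) and s).**

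| r per 14 days | Residual variance | Net gain | Range of net gain |
|---|---|---|---|
| 0 | 48.37 → 42.71 | 10.7% | 5% to 22% |
| 0.5 | 48.38 → 46.35 | 3.1% | 1% to 7% |
| 0.8 | 48.42 → 48.08 | −0.4% | −0.7% to about 0% |

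With no visit noise, the net result is the bare cost, −1.1%. A simulated two-visit MMRM (95 complete subjects, SD(b) 15, s = 50%) gave mean half-widths of 2.853 → 2.698 at r = 0, 2.864 → 2.822 at r = 0.5 and 2.852 → 2.859 at r = 0.8.

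**Visit held at Day -3.** The gap to Day 1 is then 3 days and the noise correlation r^(3/14). The net result is −0.5% to +1.0% at r = 0.5 and about −1% at r = 0.8.

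**True change during the run-in.** The model above gives Day -14 and Day 1 the same underlying level b. Protocol 9.3.1 says subjects may enter the run-in on LUM/IVA, on TEZ/IVA or on no modulator, so some may still be shifting at Day -14. Add an independent change to both Y1 and W in the middle case:
- SD 3: 48.40 → 47.24, net gain 1.3%.
- SD 5: 48.44 → 47.87, net gain 0.1%.

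**Subgroup models.** With N subjects in a category, the variance cut needed before the CI stops widening is 1 − 1/(f·q²), with f = (N − 5)/(N − 6) and q = t(0.975, N − 5)/t(0.975, N − 4). This is 1.1% at N = 95, 2.3% at 50, 4.4% at 30 and 7.7% at 20. The middle-case cut of 4.2% does not pay at 30 or fewer.

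**The case for a change.** The best case for the change is that the trade is lopsided: at worst about 1% of variance is lost, and at best about 22% is gained, with no new visit or procedure. A separate calculation supports a worthwhile upper end. Taking SD 7 as the residual SD, a partial correlation of 0.5 between Day -14 and Week 4 would cut the half-width from 2.85 to 2.47. A simulation with equal visit correlations of 0.891 kept the type I error nominal (5.1% with the term, 4.8% without). SAP section 4 allows revision before database lock, and the Week 4 difference and its CI are the primary result.

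All of that stands as arithmetic. What weakens it is that the large gains need nearly all the change variance to be independent visit noise, with no true differences in response and no change during the run-in.

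The cost also exceeds one degree of freedom:
- Subjects with a missing or invalid Day -14 value would drop out of the MMRM unless the covariate is imputed, an exception to the SAP 9.1 rule: "Incomplete/missing data will not be imputed, unless specified otherwise".
- A separate rule is needed where Day -14 already serves as baseline. The stratification fallback cannot simply be reused, since it may be a post-bronchodilator screening value taken off TEZ/IVA.
- SAP 9.3.1.5 applies the primary model within subgroups. Sparing small categories the extra term would separate the two models, and the multiple-imputation and key secondary sections would each need clarifying text.
- Protocol 12.3.3.1 and the synopsis fix the covariates. Changing them is a protocol modification under protocol 13.2.3, needing investigator and sponsor approval and submission to the regulatory authorities.

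**Conclusion.** No change is called for. The description of the plan is accurate: one pre-dose ppFEV1 is in the model, and a second is collected but left out of it. That is a legitimate choice of covariates, stated consistently in both documents, with unbiased estimation and correctly stated power.

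The expected benefit is about 0.045 points of half-width in a middle case that rests on assumed values (SD(b) 15, half the change variance noise, 14-day correlation 0.5). It falls to almost nothing with modest true change during the run-in, a late Day -14 visit or strongly correlated noise, and can become a small loss. Against that, a primary analysis that now needs no imputation would acquire an imputed covariate and several exceptions. A sponsor whose earlier data showed large, weakly correlated visit noise could reasonably choose otherwise before database lock. Nothing in these documents shows that, and keeping the planned model is equally defensible.
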